3.1.5. Immunogenicity Evaluable Population (IEP)

The IEP includes all subjects in the exposed population who:

- Have no important protocol deviation or other reason to be excluded as defined prior to database lock.
- Have not received a prohibited medication.
- Provide evaluable serum sample results for baseline and the primary immunogenicity endpoint within the required time frames:
 - Baseline: Day 1 or within 60 days before study vaccine administration
 - Day 22: Day 19 through Day 25, inclusive

In addition, all subjects in the alphavirus-naïve group are required to be seronegative for both CHIKV and VEEV at baseline, where seronegativity is defined as:

- Anti-CHIKV neutralizing antibody levels below the limit of detection (LOD) of 15, determined by luciferase-based assay (NT80)
- Anti-VEEV neutralizing antibody levels below the LOD of 20, determined by Plaque-Reduction Neutralization Test (PRNT80) assay,

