3.3. Data Handling Conventions and Transformations

By-subject listings will be presented for all enrolled subjects sorted by subject ID number, study arm, visit date, and time (if applicable). Data collected on log forms, such as AEs, will be presented in chronological order within subject.

Baseline is defined as the Day 1 value. If the Day 1 value is missing, then the last non-missing value prior to Day 1 will be used as the baseline value.

Data that are less than the limit of detection (LOD) or above the upper limit of assay reporting will be imputed as follows:

- Antibody titer assay results that are reported as less than the LOD will be imputed as the LOD/2 when calculating geometric mean titer (GMT) and geometric mean ratio (GMR). For example, if the LOD is 15 and a result is noted as “<15”, a titer of 15/2 (=7.5) will be imputed.
- For fold increase over baseline in antibody titer, if a value is < LOD, it will be imputed as the LOD. For example, if the LOD is 15 and a result is noted as “<15”, a titer of 15 will be imputed.
- A value that is one unit above the upper limit of assay reporting will be used for calculation of descriptive statistics if the datum is reported in the form of “> x” (where x is considered the limit of quantitation). Values with decimal points will follow the same logic as above.

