6.2. Secondary Immunogenicity Endpoints

Secondary immunogenicity endpoints include:

- Anti-CHIKV neutralizing antibodies, determined by luciferase-based assay (NT80), in prior alpha subjects vs. naïve alpha subjects, assessed by
 - Seroconversion rates on Days 8, 29, 57 and 182
 - GMT and GMR on Days 1, 8, 22, 29, 57 and 182
 - The proportion of subjects with titers of at least 40, 100, 160 or 640 on Days 1, 8, 22, 29, 57 and 182
- Anti-CHIKV total antibodies, determined by immunoassay, in prior alpha subjects vs. naïve alpha subjects, assessed by
 - Seroconversion rates on Days 22 and 29 where seroconversion is a 4-fold rise in titer over baseline
 - GMT and GMR on Days 1, 22 and 29

- The proportion of subjects with titers of at least 40, 100, 160 or 640 on Days 1, 22 and 29
- Anti-VEEV neutralizing antibodies, determined by Plaque-Reduction Neutralization Test (PRNT80) assay, in prior alpha subjects vs. naïve alpha subjects, assessed by
 - Seroconversion rate on Days 22 and 29 where seroconversion is a 4-fold rise in titer over baseline
 - GMT and GMR on Days 1, 22 and 29
 - The proportion of subjects with titers of at least 40, 100, 160 or 640 at Days 1, 22 and 29
- Anti-VEEV total antibodies, determined by immunoassay, in prior alpha subjects vs. naïve alpha subjects, assessed by
 - Seroconversion rate on Days 22 and 29 where seroconversion is a 4-fold rise in titer over baseline
 - GMT and GMR on Days 1, 22 and 29
 - The proportion of subjects with titers of at least 40, 100, 160 or 640 at Days 1, 22 and 29

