6.2.1. Analysis Methods for Secondary Immunogenicity Endpoints

The same method used for the primary immunogenicity analysis, excluding the estimated difference, will also be used for the secondary analysis of seroresponse rate, comparing the proportion of prior alpha subjects to the proportion of naïve alpha subjects having seroresponse by anti-CHIKV neutralizing antibodies on Days 8, 29, 57 and 182 and by anti-CHIKV total antibodies and anti-VEEV total and neutralizing antibodies on Days 22 and 29.

For the secondary analysis of GMT and GMR, the GMTs and GMRs at the specified time points will be compared for differences between the two study arms (prior alpha vs. naïve alpha) for each type of antibody listed above.

The primary model used for the immunogenicity evaluable population is an analysis of variance (ANOVA), with logarithmically-transformed (\log_{10}) titers as the dependent variable and study arm, age, and gender as the predictor variables in the model. The primary model used for the mITT population is the same except that \log_{10} baseline titer will be added as a predictor if there are subjects with measurable titers in the naïve alpha group at baseline. If any baseline titer is equal to zero, then one will be added to all baseline titers prior to taking the log. The least square means estimated from the ANOVA (or ANCOVA) and their 95% CIs will be back-transformed and reported as the group GMT values. The geometric mean ratio of the prior alpha group to the naïve alpha group, and its 95% CI, will be calculated by specifying a linear contrast between the groups in the model. Since the linear contrast yields a difference between groups in log-transformed space, the difference will be exponentiated to produce a geometric mean ratio of one group to the other. The p-value associated with each model comparison will also be reported. Additionally, the median, minimum and maximum will be summarized based on the non-transformed scale.

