An additional analysis of geometric mean of the fold-increase in titer over baseline will be provided. The geometric mean and median fold-increase in titer over baseline will be presented at each visit. To calculate the geometric mean fold-increase and 95% CI, the fold-increase results will be \log_{10} -transformed, the mean and 95% CI of these transformed data will be calculated and then exponentiated to convert to the non-transformed scale. A t-test will be used to compare the \log_{10} -transformed fold increase between the prior alpha and naive alpha subjects. The median, minimum and maximum of the fold-increase in titer over baseline will be summarized based on the non-transformed scale.

The percentage of subjects achieving specified thresholds (40, 100, 160, and 640 anti-CHIKV neutralizing antibody titers), and associated Wilson 95% CIs, will be summarized at Days 1, 8, 22, 29, 57 and 182 for anti-CHIKV neutralizing antibodies and at Days 1, 22 and 29 for anti-CHIKV total, anti-VEEV total, and anti-VEEV neutralizing antibodies. The groups will be compared by pairwise Fisher's exact tests on the percentage achieving each threshold. An additional summary will be provided for the cumulative percentage of subjects reaching the specified thresholds of anti-CHIKV neutralizing antibody titers.

All secondary analyses will be performed for the IEP. The secondary analysis of anti-CHIKV neutralizing antibodies as determined by luciferase-based assay will be repeated on the mITT population.

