6.4. Immunogenicity Subgroup Analysis

Subgroup analyses by race group – white or non-white – and gender will be conducted for the following endpoints:

- Anti-CHIKV neutralizing antibodies, determined by luciferase-based assay (NT80), in prior alpha subjects vs. naïve alpha subjects, assessed by
 - Seroconversion rates on Days 8, 22, 29, 57 and 182
 - GMT and GMR on Days 1, 8, 22, 29, 57 and 182
 - The proportion of subjects with titers of at least 40, 100, 160 or 640 on Days 1, 8, 22, 29, 57 and 18

Statistics and p-values for all sub-group analyses will be calculated using the same methods as described for the endpoint except for GMT and GMR analyses. The mean of the \log_{10} -transformed titers will be calculated and then exponentiated to convert to the non-transformed scale to estimate the GMT. 95% CIs for the GMT will be calculated by constructing a *t*-interval for the mean of the transformed titers and then back-transformed. The GMR of the prior alpha group to the naïve alpha group, and its 95% CI, will be calculated by taking the difference between groups in log-transformed space and then exponentiating the difference. *T*-tests will be used to compare \log_{10} -transformed titer data between the prior alpha and naïve alpha subjects. The median, minimum and maximum will be summarized based on the non-transformed scale.

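### For Day 1 VEEV PRNT80 in the IEP the naïve arm is constant by definition, so the single-variance ANOVA gives the prior-arm GMT a nominal 95% CI that covers about 83%

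*SAP*

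**What the plan says.** - **Who is in the IEP.** SAP 3.1.5: "all subjects in the alphavirus-naïve group are required to be seronegative for both CHIKV and VEEV at baseline". For VEEV the criterion is "Anti-VEEV neutralizing antibody levels below the LOD of 20, determined by Plaque-Reduction Neutralization Test (PRNT80) assay". It concerns baseline only and the neutralizing assay only.
- **How low results enter.** SAP 3.3 replaces a result below the LOD by half the LOD when GMT and GMR are calculated. For VEEV PRNT80 that is 20/2 = 10.
- **Which endpoints.** SAP 6.2 lists, for VEEV neutralizing antibody, "GMT and GMR on Days 1, 22 and 29".
- **Which population.** SAP 6.2.1: "All secondary analyses will be performed for the IEP". Only the CHIKV luciferase neutralization analysis is repeated on the mITT population, so the VEEV results have no second population.
- **Which model.** SAP 6.2.1 specifies for the IEP an ANOVA on log10 titer with study arm, age and gender. Then: "The least square means estimated from the ANOVA (or ANCOVA) and their 95% CIs will be back-transformed and reported as the group GMT values". A contrast in the same model gives the GMR and its CI, and a p-value is reported. No unequal-variance or censored-data option is given.
- **A different method elsewhere.** SAP 6.4 estimates subgroup GMTs with a t-interval on each group's own log titers.

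**The concern.** An ordinary ANOVA assumes one residual variance for both arms. Here the population definition and the substitution rule together set the naïve arm's Day 1 PRNT80 variance to zero. The prior arm should show real spread: any documented alphavirus vaccination qualifies (Protocol 2.8.1), and Protocol 1.1.2 reports 26% non-response to TC83. Pooling a zero-variance arm with a variable one understates the error of the variable arm.

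Three outputs are at stake: the precision stated for pre-existing VEEV neutralizing immunity in prior recipients; an interval printed for a naïve arm in which nothing was measured; and a Day 1 GMR and p-value for a contrast whose naïve side is set by the IEP rule and the imputed value.

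**Working it through.** **Inputs.** 30 per arm (SAP 1.5). LOD 20 (SAP 3.1.5). Substitution 10, or 1.0 on log10 (SAP 3.3). Model arm + age + gender, so residual df = 60 − 4 = 56 (SAP 6.2.1). The prior-arm SD of log10 titer, σ, is not in the documents; it cancels from coverage when the naïve SD is 0.

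**The plan's own figure.** Simulating the SAP model with equal SDs (0.6 in both arms, 8,000 trials) gives 94.6% coverage of the prior-arm GMT, so the nominal 95% is sound when its assumption holds.

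**Prior-arm GMT, naïve SD = 0.** Leaving aside the two covariate terms:
- pooled variance = (29σ² + 29·0)/58 = 0.50σ²
- large-sample coverage = 2Φ(1.96·√0.50) − 1 = 83.4%
- with t quantiles: critical value 2.003 on 56 df, 2.003·√0.50 = 1.416, and 2·T₂₉(1.416) − 1 = 83.3%
- simulation of the full model: 83.7%, 83.5% and 83.9% at σ = 0.4, 0.6 and 0.9
- with 26% of the prior arm also placed at LOD/2: 84.1%, so normal titers are not required
- interval from the prior arm's own data (29 df): 95.0%

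**Width, assuming σ = 0.5 log10.**
- Model half-width: 2.003·0.5·√0.50/√30 = 0.129, a factor of 1.35.
- Own-arm half-width: 2.045·0.5/√30 = 0.187, a factor of 1.54.
- 0.129/0.187 = 0.69, so the interval is about 31% too narrow on the log scale.
- A naïve arm entirely below 20 would be printed as GMT 10 with a CI of 10/1.35 to 10·1.35, about 7.4 to 13.5.

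**Days 22 and 29.** The naïve SD is not fixed by the IEP rule. With prior SD 0.6 and 30 per arm:

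| Naïve SD | Coverage, prior-arm GMT |
|---|---|
| 0 | 83.5% |
| 0.15 | 85.1% |
| 0.30 | 88.4% |
| 0.60 | 94.6% |

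**GMR interval, naïve SD = 0.** The true variance of the log difference is σ²/n₁, where n₁ is the prior arm and n₀ the naïve arm. The model uses s²(1/n₁ + 1/n₀). At 30/30 this is 0.50σ²·(2/30) = σ²/30, which is correct. Coverage falls just short of 95% only because 56 df are used where 29 apply.

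| Prior/naïve | Coverage, prior-arm GMT | Coverage, GMR |
|---|---|---|
| 30/30 | 83.5% | 94.4% |
| 30/25 | 85.6% | 96.4% |
| 30/20 | 87.1% | 97.9% |
| 25/30 | 81.4% | 91.7% |
| 20/30 | 78% | 88% |

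**GMR and the substituted value.** On Day 1 the GMR is essentially the prior GMT divided by 10. For a prior GMT of 200 with no prior subject below the LOD, it is 200/10 = 20 with LOD/2, 200/14.14 = 14.1 with LOD/√2, and 200/20 = 10 with LOD. If a fraction f of the prior arm is below the LOD, moving from LOD/2 to LOD multiplies the GMR by 2^f/2 = 2^(f−1): 0.50 at f = 0, and 0.60 at f = 0.26.

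**The case against.** The strongest reply is that the problem is narrow. Several wider readings are tempting, and the documents do not support them.

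- **All VEEV GMT intervals cover 83%.** Seronegativity is required at baseline only. Whether the vaccine induces responses to other alphaviruses is one of the study's own questions (Protocol 1.3), so naïve titers on Days 22 and 29 may vary, and under-coverage shrinks as they do.
- **VEEV total antibody is affected too.** It is a separate endpoint with no seronegativity rule and no stated LOD. Zero variance does not follow.
- **Day 1 CHIKV has the same fault.** The naïve arm is indeed fixed at 15/2 = 7.5. But exclusion criteria 6 and 13 also keep people with natural alphavirus infection or a prior chikungunya vaccine out of the prior arm, which may sit largely at 7.5 as well. Under-coverage needs prior-arm spread, and none is shown.
- **The GMR interval is generally wrong.** At the planned 30/30 it is close to nominal. Excluding seropositive naïve subjects makes that arm the smaller one, which errs on the conservative side. The opposite imbalance can still occur: under Protocol 4.18 a matched control may stay after a prior recipient withdraws.
- **The assessment of boosting rests on these intervals.** SAP 6.2.1 also gives geometric mean fold-increases with their own CIs and seroresponse rates with Wilson CIs. Day 1 immunity is also described by threshold proportions, median and range.

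LOD/2 is also an openly pre-specified convention, and choosing it is not an error. All these limits stand. They leave intact the Day 1 PRNT80 result, which follows from the SAP's rules whenever the prior arm varies.

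**Conclusion.** The concern holds for VEEV PRNT80 in the IEP. On Day 1 the naïve arm is constant by construction. With about 30 per arm and any real spread in the prior arm, the reported 95% CI for the prior-arm GMT covers about 83%, whatever the size of that spread. The naïve arm's interval has no meaning. On Days 22 and 29 the figure is again about 83% if every naïve titer stays below 20, and between about 83% and 95% if some rise. The GMR interval is adequate at equal arm sizes, falls to about 88% at 20 prior/30 naïve, and is conservative when the naïve arm is the smaller. The Day 1 GMR depends on the substituted value by up to a factor of two between LOD/2 and LOD. The Day 1 p-value compares the prior arm with a value that the population definition fixes.

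These are secondary endpoints. VEEV total antibody, Day 1 CHIKV and the primary Fisher comparison are not shown to be affected. The widths quoted assume a prior-arm SD of 0.5, and the Day 22/29 figures assume 0.6.

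**What to change.** For the VEEV PRNT80 GMT and GMR in the IEP:

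1. Keep arm, age and gender in the model, but allow a separate residual variance per arm with matching degrees of freedom. Alternatively, use each arm's own t-interval, as SAP 6.4 already does for subgroups.
2. When every result in an arm is below the LOD, report that arm as all <LOD with no CI, and take the prior-arm CI from the prior arm alone. A two-variance model cannot be fitted sensibly to a constant arm, so this case needs its own rule. Age and gender can still be adjusted for within the prior arm.
3. Label the GMR as dependent on LOD/2. The prior GMT divided by the LOD should not be presented as a lower bound, because the prior GMT may itself contain substituted values.
4. Omit the Day 1 between-arm p-value.

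The cost is SAP wording, a small programming change and a wider prior-arm interval; at an assumed SD of 0.5 the factor goes from 1.35 to 1.54. The first SAP addendum refers to decisions made after database lock. If the tables already exist, this can be added as a supplementary table, identified as specified after lock.

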9 STATISTICAL ANALYSIS

9.1 Sample Size Calculation

The sample size here was chosen based on the number of subjects in the Fort Detrick Special Immunization/Special Procedures Program (USAMRIID) who are available for screening. Of the approximately 60 available, 30 are expected to enroll in this trial along with an equal number of alphavirus naïve age- and gender-matched subjects. Based on an interim analysis of this vaccine lot and regimen in Study PXVX0317-001, at least 95% of the alphavirus-naïve controls are expected to seroconvert in this trial. Assuming that the alphavirus-naïve group has a 95% seroconversion rate, a total sample size of 60 subjects affords 80% power to detect a significant difference between groups if the seroconversion rate in the prior alphavirus vaccine recipients is 65% or less. Or, in other words, power is 80% to detect a difference between groups if the seroconversion rate in the prior alphavirus recipients is 30 percentage points lower than in the alphavirus-naïve group. Compared to the previously cited studies in which decrements in the proportion of seroconversion of 64% (McClain 1998) and 100% (Harrison 1971) (DeMeio 1979) were seen, this study is adequately powered to detect immune interference on the order of one-half to one-third of what has previously been described.

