9.3 Treatment Groups

Subjects will all receive the same vaccine regimen in an open label fashion. There will be no randomization and no blinding as the primary endpoint (immune response at Day 22) is not subject to subjective interpretation. The participants themselves already know whether or not they have previously received another alphavirus vaccine as such vaccines have only been available through IND and their administration required informed consent. The safety profile of this vaccine is well-established for a phase 2 candidate and is not expected to differ between the two groups enough to justify the inclusion of a placebo group. Laboratory workers at USAMRIID have been exposed to multiple alphavirus and other vaccines in the past without evidence of any clinically significant adverse health effects ([Pittman 2004](#)).

Subject matching will be done by age (± 3 years) and gender, both of which have been shown to play roles in vaccine immunogenicity in general ([Klein 2016](#)) and alphavirus immune interference in particular ([Reisler 2012](#)), ([Pittman 2009](#)).

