9.6 Immunogenicity Analysis

All tests will be carried out at a 2-sided significance level of 0.05 and no adjustment for multiplicity will be applied.

Seroconversion Analysis:

The primary immunogenicity analysis will compare prior alphavirus vaccine recipients to alphavirus-naïve controls on the proportion in each group who seroconvert by anti-CHIKV neutralizing antibody at Day 22. Seroconversion is defined as a 4-fold or greater rise over baseline in anti-CHIKV neutralizing antibodies as assessed by a luciferase-based assay.

Specifically, we will test the hypotheses:

$$H_0: P_1 = P_2 \text{ vs. } H_1: P_1 \neq P_2$$

where P_1 and P_2 denote the proportion of subjects who seroconvert in the prior alphavirus vaccine recipients and the alphavirus-naïve controls, respectively.

The significance of the comparison of the pre-exposure groups will be assessed using a Fisher's exact test. The percentage who seroconvert in each group will be presented along with its 95% CI calculated using the Wilson method. A sensitivity analysis of the comparison will be performed using a logistic regression model that incorporates age, gender, and baseline titer as potential predictive factors. Fisher's test comparing seroconversion rates at other time points may also be performed. Similar analyses of the proportion who seroconvert will be conducted on Days 8, 29, 57 and 182 for anti-CHIKV neutralizing antibody and on Days 22 and 29 for total anti-CHIKV, total anti-VEEV and neutralizing anti-VEEV antibodies (secondary endpoints).

Threshold analyses:

The percentage of subjects achieving specified thresholds (e.g., ≥ 40 , 160, and 640 anti-CHIKV antibody titers), and associated Wilson 95% CIs, will also be calculated for Days 1, 8, 22, 29, 57 and 182 for neutralizing antibody and at Days 1, 22 and 29 for total anti-CHIKV, total anti-VEEV and neutralizing anti-VEEV antibodies (secondary end-points). The groups will be compared by pairwise Fisher's exact tests on the percentage achieving each threshold.

GMT analyses:

For the secondary comparisons based on GMT, the hypotheses tested will be

$$H_0: \mu_1 = \mu_2 \text{ vs. } H_1: \mu_1 \neq \mu_2$$

where μ_1 and μ_2 denote the GMT for the prior alphavirus vaccine recipients and the alphavirus-naïve controls, respectively.

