1.5. Sample Size and Power

The sample size here was chosen based on the number of subjects in the Fort Detrick Special Immunization/Special Procedures Program (USAMRIID) who are available for screening. Of the approximately 60 available, 30 are expected to enroll in this trial along with an equal number of alphavirus naïve age- and gender-matched subjects. Based on an interim analysis of this vaccine lot and regimen in Study PXVX-CV-317-001, at least 95% of the alphavirus-naïve controls are expected to seroconvert in this trial. Assuming that the alphavirus-naïve group has a 95% seroconversion rate, a total sample size of 60 subjects affords 80% power to detect a significant difference between groups if the seroconversion rate in the prior alphavirus vaccine recipients is 65% or less. Or, in other words, power is 80% to detect a difference between groups if the seroconversion rate in the prior alphavirus recipients is 30 percentage points lower than in the alphavirus-naïve group. Compared to the previously cited studies in which decrements in the proportion of seroconversion of 64% (McClain 1998) and 100% (Harrison 1971) (DeMeio 1979) were seen, this study is adequately powered to detect immune interference on the order of one-half to one-third of what has previously been described. Further details of sample size and power estimation can be found in Section 9.1 of the protocol.

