For the comparison against 181/25, for each participant at each time point, the raw heterologous strain titer will be divided by the 181/25 strain titer to provide a raw fold difference. Descriptive statistics will be provided and statistical significance between the treatment groups will be based on a t-test.

As the titers and fold differences are not necessarily normally distributed, an additional analysis of geometric mean of the fold-increase in titer versus strain 181/25 will be provided. To calculate the geometric mean fold-increase and 95% CI, each strain titer will be log₁₀-transformed and the difference versus 181/25 strain computed (other strain minus 181/25 strain). The mean and 95% CI of the differences in the logs will be calculated and then exponentiated to convert to the non-transformed scale. A t-test will be used to compare the log₁₀-transformed difference in log titers between the prior alpha and naïve alpha subjects.

Changes to the safety dataset structures

The original CDISC datasets were based on a flat structure (each symptom per day per participant was its own record). The FDA OVRR guidance requires that the CE dataset for the data based on the diaries have a summary structure similar to the AE data (start and stop of the event) and that any event that carried past the diary collection be summarized with the diary data rather than as an AE. Per the protocol directions, if an event recorded on the diary continued past day 8, the event was to also be recorded as an AE. These data need to be copied to the CE data to reflect the full extent of the diary symptom duration.

As a result, the datasets that comprise the adverse event CDISC domains (AE and CE), need to be updated to reflect the FDA's guidance.

The changes needed are:

AE data

- STDM - leave the diary records in AE.
- Copy the events that start before Day 8 post injection to FACE (turn into flat structure - one record per event per day)
- Set flag in SUPPAE that this is record that was moved.
- Add same flag to ADaM ADAE dataset to exclude this data from the AE summaries to avoid double counting.

CE data

- Copy flat structure from CE to FACE domain.
- Combine the transferred AE data with the 'new' FACE data (see above) to produce a new summary CE record.
- CEDUR should consist of the dates from the CE and AE records combined (per pre-BLA response from FDA) to provide the full duration across the diary collection and into the AE collection time period.

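### SAP 6.2.1 tests log10 fold-increase with an unadjusted t-test although the arms are matched on age and gender and the GMT model adjusts for both; if those factors act alike in both arms, precision is lost

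*SAP*

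**What the plan says.** **Matching.** Protocol 9.3 states: "Subject matching will be done by age (± 3 years) and gender, both of which have been shown to play roles in vaccine immunogenicity in general". The same sentence adds that both factors also bear on alphavirus immune interference. The Protocol synopsis and SAP 1.4 explain that the matching is for group comparability and does not link individuals for analysis.

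**GMT and GMR.** SAP 6.2.1 models log10 titer with "study arm, age, and gender as the predictor variables in the model". In the immunogenicity evaluable population (IEP) the model has no baseline term. Log10 baseline titer can enter only in the mITT population, and only under a stated condition.

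**Fold-increase.** The same section adds a further analysis, a t-test of the log10 "transformed fold increase between the prior alpha and naive alpha subjects", with no covariates. The SAP table list gives fold-increase tables for CHIKV and VEEV, neutralizing and total antibody.

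**Addendum 2, section 2.** GMTs against the heterologous CHIKV strains use the model with arm, age and gender. The comparison with strain 181/25 uses t-tests, once on the raw ratio and once on the log10 "transformed difference in log titers between the prior alpha and naïve alpha subjects".

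Neither document says why some continuous comparisons are adjusted and others are not.

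**The concern.** Matching on a prognostic factor removes that factor from the difference between arm means. An analysis that then ignores the factor leaves its variance in the error term, so the standard error is larger than the true variability of the difference. The confidence interval is too wide and the test rejects too rarely.

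This matters most for VEEV. One of the study's two questions (Protocol 1.3) is whether the vaccine boosts existing immunity to other alphaviruses. VEEV and total-antibody data are analysed only in the IEP. There, naïve subjects must be VEEV-seronegative at baseline (SAP 3.1.5) but prior recipients need not be, so a post-vaccination VEEV GMR mixes old immunity with any new rise. The fold-increase t-test is the only continuous between-arm test of the rise itself.

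**Working it through.** **Plan's own figure.** The documents give no power for the t-tests. Their only stated power is for the primary Fisher test: "a total sample size of 60 subjects affords 80% power to detect a significant difference between groups", for 95% against 65% seroconversion. Exact enumeration with 30 per arm gives 78.8%, which agrees with 80% to within 2 points. It does not depend on anything below.

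**Inputs from the documents.** Tests are two-sided at 0.05 without multiplicity adjustment (Protocol 9.6). There are 30 subjects per arm (SAP 1.5: "30 are expected to enroll in this trial along with an equal number of alphavirus naïve age- and gender-matched subjects"), and matching is on gender and on age within 3 years.

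**Assumptions.** R² is the share of log10 fold-increase variance explained by age and gender. The documents give no value, so a range is used. The true difference is 0.736 SD, at which an ordinary two-sample t-test with 30 per arm has 80% power; 0.5 SD is a second case. Total SD is 1 in each arm, and age and gender contribute equally.

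**Formula.** With close matching and effects shared by both arms, the true variance of the difference in means is 2σ²(1 − R²)/n. The t-test estimates 2σ²/n. Hence:

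- true size of the t-test ≈ 2[1 − Φ(1.96/√(1 − R²))]
- CI width relative to the adjusted model ≈ 1/√(1 − R²)

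At R² = 0.2, √0.8 = 0.894 and 1.96/0.894 = 2.19, so the size is about 2.8% and the interval is 1/0.894 = 1.12 times as wide.

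**Simulation, shared effect** (20,000 trials per setting; t-test against the linear model on arm, age and gender):

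| R² | Size, t-test / adjusted | Power at 0.736 SD | Power at 0.5 SD | CI wider by |
|---|---|---|---|---|
| 0 | about 5% / 5% | 80% / 80% | 48% / 48% | 0% |
| 0.05 | 4.1% / 4.6% | 81% / 82% | 48% / 50% | 3% |
| 0.1 | 3.8% / 4.9% | 81% / 84% | 48% / 52% | 5% |
| 0.2 | 2.9% / 5.0% | 83% / 88% | 48% / 57% | 12% |
| 0.3 | 2.0% / 4.9% | 84% / 92% | 48% / 62% | 20% |

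With the same R² of 0.2 but no matching, the t-test's size is 5.0%, so the conservatism comes from the matching.

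**Simulation, effect in prior recipients only** (equal SDs; 10,000 trials per setting). At a share of 0.2, the t-test's size is about 5% and power is 80% against 81%. At 0.3, its size is 5.2% and power is 79.6% against 81.4%, while the equal-variance adjusted model's size is 6.1%.

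**Simulation, sharply unequal variances** (naïve SD one-tenth of the prior-arm SD, share 0.2 in the prior arm only). The t-test's size is 5.4%; that of the equal-variance adjusted model is 6.6%.

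**CHIKV in the IEP.** SAP 3.1.5 requires naïve subjects to be below 15 at baseline, and SAP 3.3 sets such values to 15 for fold-increase. Their log10 fold-increase is therefore log10(titer) − log10(15), a shift by a constant. Any age and gender effect on the titer carries over, so the t-test is close to an unadjusted version of the adjusted GMR test.

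**The case against.** The strongest objection is that the loss depends on a shared effect, which the documents do not establish. Protocol 9.3 also ties age and gender to immune interference, which can occur only in prior recipients. In that case the conservatism disappears, the gain is 1 to 2 points, and an equal-variance adjusted model can run above 5%. VEEV is where a shared effect and equal variances are least secure, because naïve subjects start seronegative and may respond little. This stands. It limits the claim and shapes the fix.

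The stakes are also modest. Fold-increase is an additional analysis and is not among the listed secondary endpoints, the 181/25 ratio is exploratory, and no decision rule uses either p-value. For CHIKV neutralizing antibody the adjusted GMR is already reported. This stands too.

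The statement that individuals are not paired is a good argument against a paired test. It is no argument against covariate adjustment, which the SAP already uses for GMT. Replacement (Protocol 4.18) and IEP exclusions can loosen the matching, which also favours adjustment over pairing.

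A reader might infer two stronger points that the documents do not support:

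- **That the strain comparison in Addendum 2 is unadjusted as a whole.** The strain GMTs are adjusted; only the ratio to 181/25 is not. That ratio is within-subject, so age and gender effects common to both strains cancel and the loss may be small.
- **That the two CHIKV p-values can differ only through the matching factors.** SAP 3.3 imputes values below the limit of detection as 7.5 for GMT but 15 for fold-increase, and prior recipients may have measurable baselines. Either can also separate them.

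**Conclusion.** The inconsistency is real and unexplained. For age and gender effects shared by both arms, the unadjusted t-test on log10 fold-increase is conservative and less precise than the model the SAP uses for GMT. At 0.736 SD the power difference is about 3, 5 and 8 points for an assumed R² of 0.1, 0.2 and 0.3. It is negligible at 0.05 or less, and about 1 to 2 points if the effect is confined to prior recipients. All of these R² values are assumptions.

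The loss is relative to the adjusted model: at 0.736 SD the t-test's power stays at about 80% or above throughout. A reader might conclude that the t-test is invalid or inflates false positives, but in these checks its size was at or below about 5%. Nor does the point reach the primary Fisher test, which was sized as a comparison of two groups. This is a worthwhile gain in precision and consistency, chiefly for the VEEV rise, and it does not threaten the main conclusions.

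**What to change.** **SAP 6.2.1.** Compare log10 fold-increase with a linear model on study arm, age and gender. Report the back-transformed ratio of geometric mean fold-increases with its 95% CI and p-value. Keep the per-arm descriptive summaries. Do not use a paired test.

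**VEEV.** Use heteroscedasticity-robust standard errors or arm-specific variances, because the arms' variances may differ. This should reduce the excess size seen with the equal-variance model but may not remove all of it if age and gender act in one arm only.

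**Addendum 2.** For consistency, apply the same model to the log10 difference versus 181/25 (Table 14.2.6.4 only), expecting a small gain.

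**Timing.** SAP section 8 describes models already attempted, and Addendum 1 records a decision made after database lock. If results are already known, label the adjusted analysis as added later and show it beside the specified t-test.

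**Cost.** One sentence in each document, a small programming change that reuses the GMT model, and two error degrees of freedom (60 − 2 = 58 becomes 60 − 4 = 56). No new data are needed.
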